## 8 Study Intervention

Subjects (n=10) will be exposed to the Solius Photobiological System which includes exposure to visible purple LEDs and invisible UVB radiation. The study intervention will involve an investigational UVB emitting device, The Solius Photobiologic System created by Solius. The Solius Photobiological System emits UVB. To make sure subjects do not develop redness, the exposure will set for the lamp to 60% or 0.60 of the minimal erythema dose (MED) for each individual's skin type.

As the appropriate doses are individualized to the subject, to establish the correct dose, each subject will complete a titration period of up to 5 weeks. The titration period will start with an erythema weighted dose of 10.53 mJ/cm^2 to 43.07 mJ/cm^2 (depending on skin type) and increase by 26 – 36% each step until a maximum erythema weighted dose of 34.88 mJ/cm^2 – 109.33 mJ/cm^2 (depending on skin type) or the subject shows a skin reaction. This dose will be the subject's dosage.

The device will have a strip of purple LEDs installed inside the light towers. Both UV lamps and purple LEDs will turn on during the treatment. According to a previous study by Solius where 43 subjects were exposed to a 0.6 MED, the stimulation of cutaneous vitamin D and subsequent increase in serum concentrations of 25(OH)D from phototherapy was compared to the effect of a Recommended Daily Allowance (RDA) based dose of 600 IU vitamin D3 supplement daily for 10 weeks. Thus, we will expose these individuals a 0.6 MED once per week for 4 weeks to observe the effect on 25(OH)D serum concentration.

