## 2 Protocol Summary

Title:	Evaluating the effect of Solius Photobiological System in improving serum levels of 25-hydroxyvitamin D in vitamin D deficient/insufficient adults: A feasibility study
Population:	Healthy adults ages 22 years and older; both sexes, approximately 14 adults for serum 25-hydroxyvitamin D screening, 10 adults with vitamin D deficiency/insufficiency for the feasibility study
Intervention:	The study treatment is a weekly exposure to the Solius Photobiological System, which emits Ultraviolet B Radiation (UVB). This will be accomplished with an established dose of UVB radiation for 4 weeks. SOLIUS delivers 0.6 Minimal Erythema Dose (MED) to achieve non-perceivable erythema for a therapeutic dose.
Objectives:	To assess the safety and effectiveness of the Solius Photobiological System in improving serum levels of 25-hydroxyvitamin D in vitamin D deficient/insufficient adults of various skin types
Design/Methodology:	We will conduct an interventional study to determine the changes in serum 25-hydroxyvitamin D levels in subjects who received Ultraviolet B Radiation (UVB) generated by the Solius Photobiological System for 4 weeks. Subjects will first undergo an evaluation of each individual's sensitivity to the Solius Photobiological System UVB using the device titration system for the first 5 weeks. Once determined after the 5 weeks, the subjects will be enrolled in a 4-week study where they will be exposed to their individualized titration evaluation. Approximately 14 adult subjects will be enrolled for serum 25-hydroxyvitamin D screening. We expect to enroll 10 vitamin D-deficient or insufficient subjects in this study. Serum 25-hydroxyvitamin D levels will be measured prior to the first titration (week 2), prior to the intervention (week 6) and after end of the study, and the changes in serum 25-hydroxyvitamin D levels will be analyzed. We expect that the levels will increase from the baseline.
Total Study Duration:	6 months

---

**Subject Participation Duration:** 10 weeks including one week for screening, 5 weeks for titration, 4 weeks for intervention

---

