The subject's dosage will be administered under conditions of full-body exposure (males in swimming trunks or briefs and females in bikini or bra and panties) of 0.6 minimal erythema dose (MED) once per week for 4 weeks. At each visit, the subject will report adverse events and any skin changes.

We will have the blood samples drawn by trained professionals to minimize the risk of hematoma formation, bleeding, or infection at the site of needle insertion. Study staff will update subjects in a timely way on any new information that may affect their health, welfare, or decision to stay in this study. Any and all side effects reported will be recorded in the subjects' file in the study binder. Subjects will be instructed to call the study staff or PI immediately if any side effects do occur. The PI will advise the subjects according to the symptoms reported. After the determination, all samples will be de-identified. The PI will be available to answer any questions or concerns from potential subjects prior to consenting. We have a plan to protect subject privacy and confidentiality, which is explained in the plan to protect subject privacy and confidentiality in the data section.

Vitamin D deficiency and insufficiency is common in adults due to an inadequate dietary intake of vitamin D and or inadequate sun exposure. Chronic vitamin D deficiency and insufficiency can lead to bone loss resulting in increased risk of fracture later in life. Chronic vitamin D deficiency can also cause a mineralization defect of the skeleton resulting in osteomalacia. Short term (10 weeks) vitamin D deficiency and insufficiency is not associated with significant bone loss or osteomalacia. Therefore, the participants are at no increased risk for fracture or osteomalacia. At the termination of this study those participants will be encouraged to take a vitamin D supplement along the guidelines recommended by the Endocrine Society to correct their vitamin D deficiency and insufficiency.

Chronic excessive exposure to sunlight or ultraviolet radiation for prolonged periods of time, in years or decades, can increase risk for nonmelanoma skin cancer. To minimize the risk the subjects will be 22 years and older and will be exposed to suberythemal doses of UVB radiation for the duration of the study

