### 6.3 Analysis of Risks in Relation to Benefits

Highly trained professionals will be performing the blood draws which is likely to be a chance of risk. The adverse skin reaction from the Solius Photobiological System such as skin erythema and pruritus is a possible risk in this study. However, this study will expose the participants to a relatively low intensity of UVB (0.6 MED), so the risk of adverse reaction is minimal. All the participants will be asked for their willingness to receive the intervention at every exposure and will be questioned and examined for any potential adverse reaction due to the intervention. If any significant adverse reaction is detected, the intervention will immediately stop and the affected participant will receive immediate medical attention. Significant adverse reactions include photokeratitis, moderate to severe skin tenderness, itchiness and tightening, skin blistering, or bruising or tearing of skin. The risks of breach of confidentiality are highly unlikely, and therefore benefits will greatly outweigh the risks.

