## 10.2 Safety Review

[name] or [name] will interview the subjects before their next exposure each week for any adverse events including erythema or any other skin reactions as shown in the table. At the time of the evaluation, it will be determined whether the subject will continue with the next exposure or whether the subject will be removed from the study. This will be based on the determination of the degree of erythema or adverse skin reaction. [name] will serve as an Independent Scientific Reviewer (ISR). He will provide an assurance that the findings and conclusions reached are supported by the data presented, and also, to assure that the content is consistent with applicable scientific standards and will be responsible for a review of the data analysis, data interpretation and/or presentations and manuscripts.

The following known side effects of UVB will be monitored:

Side effect	Signs/symptoms	Instruction for subjects on monitoring
Sunburn	Pain, tenderness of the skin, redness, tightness, itching, and rarely blistering	Check for pain and redness 4-6 hours after treatment. If there is severe pain, should seek medical attention.  If there are blisters, should seek medical attention
Photoaging	Atrophic skin, coarseness, fibrotic areas, increased fragility, laxity, mottled pigmentation, telangiectasias, wrinkling	If there is increased fragility (i.e. easy bruising or tearing of skin), then should seek medical attention. The other photoaging side effects are benign and more of a cosmetic nature.
Tanning	Skin darkening	As a benign side effect, no subject monitoring is needed

In addition, Prior to each treatment, Solius software will prompt the user with the following questions to assess erythema:

1. *Did you observe any pinkness (similar to sunburn) after your last treatment? (yes / no)*
2. *Did the pinkness last for more than 3 days? (yes / no)*
3. *Did you experience any pain or discomfort (excluding itch) with the pinkness? (none / mild / moderate/severe)*

Based on the user's response, the software could maintain current dose, reduce dose, or block account for further investigation. The PI or [name] or [name] will be notified to perform further assessment if an account was blocked by the software.

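### When titration stops on a skin reaction, the dosing rule makes the reaction dose the weekly treatment dose, contrary to the plan's 0.6 MED, no-redness and withdrawal statements

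*Combined protocol and SAP*

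**What the plan says.** Sections 6.1 and 8 describe the same titration. It starts at an erythemally weighted dose of 10.53 to 43.07 mJ/cm², by skin type. The dose rises 26 to 36% a step until it reaches a skin-type maximum of 34.88 to 109.33 mJ/cm² "or the subject shows a skin reaction. This dose will be the subject's dosage". No step-down or multiplier follows.

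Section 8 also sets the lamp at "60% or 0.60 of the minimal erythema dose (MED) for each individual's skin type", with the declared aim of avoiding redness, and concludes: "we will expose these individuals a 0.6 MED once per week for 4 weeks to observe the effect on 25(OH)D serum concentration". Section 6.1 uses the same term for both doses: "The subject's dosage will be administered under conditions of full-body exposure", and later in that sentence "of 0.6 minimal erythema dose (MED) once per week for 4 weeks". Section 2 adds: "SOLIUS delivers 0.6 Minimal Erythema Dose (MED) to achieve non-perceivable erythema for a therapeutic dose". Section 6.1 closes by saying that exposure stays below the erythema threshold for the whole study, and Section 6.3 rests its minimal-risk judgement on 0.6 MED.

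Reactions are handled in three further places:

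- **Section 10.2.** Staff ask before each exposure "for any adverse events including erythema or any other skin reactions as shown in the table" and decide by degree whether the subject continues or is removed. The software asks about pinkness and may keep the dose, lower it or block the account.
- **Section 6.3.** A list of significant reactions, such as blistering and photokeratitis, stops the intervention at once.
- **Section 10.4.** An adverse reaction to the light leads to withdrawal. Erythema and pruritus are the examples; there is no severity threshold and no exemption for titration.

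**The concern.** A dose that has just produced a skin reaction is not a dose chosen to prevent one. Followed literally, the rule gives a reactor four weekly full-body exposures at a level the rest of the plan says it will not use. Section 10.4, followed literally, removes the same subject before any treatment dose is needed.

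Three things are at stake:

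- **Safety description.** The statements in Sections 2, 6.1 and 6.3 would not describe a reactor who continues at that dose.
- **Interpretation.** A 25(OH)D change reported as the effect of weekly 0.6 MED would include a subject treated on a different basis. With about 10 subjects, each one is 10% of the sample.
- **Purpose.** Section 3.2 presents this study as preparation for a larger one. A dosing rule that can be followed in only one way is part of what it should deliver.

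**Working it through.** **1. Does the titration ladder hold together?** Inputs are the start doses, maxima and step range (Section 8) and five titration visits (Section 9), hence four increments. Pair the lowest start with the lowest maximum and the highest with the highest (an assumption). Step = (maximum/start)^(1/4) − 1.

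- Lowest: (34.88/10.53)^(1/4) − 1 = 3.312^(1/4) − 1 = 34.9%.
- Highest: (109.33/43.07)^(1/4) − 1 = 2.538^(1/4) − 1 = 26.2%.

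Both fall inside the stated 26–36%. The ladder is consistent; the difficulty lies in which dose is carried forward.

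**2. Reaction dose on the subject's own MED.** Assume that the reaction is threshold erythema, MED is stable over the titration weeks, the reaction comes after the first step, and neither staff nor software reduces the dose. Own MED then lies above the previous dose and at or below the reaction dose. With step ratio g = 1.26 to 1.36, reaction dose/MED runs from 1.00 up to g.

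- g = 1.26: 1.00 to 1.26; divided by 0.6, 1.67 to 2.10.
- g = 1.36: 1.00 to 1.36; divided by 0.6, 1.67 to 2.27.

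For a reaction at the first step there is no earlier dose, so the ladder gives no upper bound.

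**3. If the dose carried forward was meant to be the last one tolerated.** The ratio runs from 1/g up to 1.00.

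- g = 1.26: from 0.79 of own MED, or 1.32 times 0.6.
- g = 1.36: from 0.74 of own MED, or 1.23 times 0.6.

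The upper end is 1.00, or 1.67 times 0.6. This reading does not give 0.6 either. A factor of 0.6 lies ln(1/0.6)/ln(g) steps below the reaction dose: 1.66 steps at g = 1.36 and 2.21 at g = 1.26.

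**4. Reaction dose on a nominal skin-type scale.** Suppose that each maximum is 0.6 of a skin-type MED. The implied MEDs are 34.88/0.6 = 58.1 and 109.33/0.6 = 182.2 mJ/cm². With equal-ratio steps the ladders are:

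| Step | 1 | 2 | 3 | 4 | 5 |
|---|---|---|---|---|---|
| Lowest (mJ/cm²) | 10.53 | 14.21 | 19.16 | 25.85 | 34.88 |
| Nominal fraction | 0.18 | 0.24 | 0.33 | 0.44 | 0.60 |
| Highest (mJ/cm²) | 43.07 | 54.36 | 68.62 | 86.62 | 109.33 |
| Nominal fraction | 0.24 | 0.30 | 0.38 | 0.48 | 0.60 |

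On this scale a reactor who stops before the maximum is below 0.6, and a subject at the maximum is at 0.6. The documents give no skin-type MED values, so the supposition cannot be checked.

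**5. What happens to a subject with mild erythema during titration?**

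- Sections 6.1 and 8: the dose becomes the treatment dose.
- Section 10.2, staff: continue or remove, by degree.
- Section 10.2, software: keep, reduce or block, with no stated mapping from answers to action.
- Section 10.4: withdraw.

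No text says which prevails.

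**The case against.** The strongest reply is that Section 8 ties 0.6 to the MED for the skin type, not to an individually measured MED. On that scale an early reactor is below the label, as step 4 shows. This stands against the multiples: a reader might infer that reactors will be treated at about 1.7 to 2.3 times the stated dose, and the documents do not support that as an expected dose. It does not rescue the rule, because a reaction dose conflicts with the no-redness and below-threshold statements on either scale.

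The second reply is that Section 10.2 provides a graded staff decision and a software check on pinkness before each exposure. This is a real safeguard, and it would be wrong to say that the plan has none. But it is permissive: keeping the current dose is one permitted response and leaves the reaction dose in place, while Section 10.4 has no grading.

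The third reply is that skin reaction in the titration rule and adverse reaction in Section 10.4 need not mean the same thing. That is possible, but the former is undefined, Section 10.2 counts erythema among skin reactions, and Section 10.4 names both erythema and pruritus.

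A reader might also infer that subjects at the maximum are mis-dosed, or that a separate MED test is missing. Neither follows. The maxima and the 0.6 label are both given by skin type and may coincide, and Section 2 describes titration as the evaluation of individual sensitivity.

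**Conclusion.** The rule is wrong as written on one branch: subjects whose titration stops on a skin reaction. For them Sections 6.1 and 8 prescribe a dose that conflicts with Sections 2 and 6.1 and with Section 8's own aim, and Section 10.4 would remove them. That conclusion rests on the wording and is firm.

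Its size is conditional. Under the assumptions in step 2 the dose is 1.00 to 1.26–1.36 of own MED; on the nominal scale a reaction before the maximum gives less than 0.6. For subjects who reach the maximum without a reaction there is no error.

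The paired comparison in Section 12.1 and the sample size in Section 12.3 (difference 6, standard deviation 4) contain no dose term and are unaffected. What is affected is the description of the regimen and its safety. The documents do not indicate how many subjects will react; it may be none.

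**What to change.** In Sections 6.1 and 8, limit the carry-forward sentence to subjects who reach the maximum without a reaction. For subjects who stop on a reaction, state a lower treatment dose consistent with the plan's own factor. One example is 0.6 times the reaction dose, which under the step 2 assumptions is 0.6 × (1.00 to 1.26–1.36) = 0.60 to 0.76–0.82 of own MED. Define skin reaction for titration. In Section 10.4, say that a mild titration reaction leads to this reduction and that the significant reactions listed in Section 6.3 lead to withdrawal, and align Section 10.2 with it.

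If the sponsor keeps the present rule, remove the 0.6 MED and below-threshold statements for reactors. Report the 25(OH)D change as the effect of a titrated, skin-type-capped dose, and list for each subject why titration stopped and what dose was delivered.

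The cost is a few sentences and, under the alternative, one listing for about 10 subjects. Section 9 says the software already holds dosing profiles. The downside is that a reactor may receive less UVB, sometimes below the starting dose: on the lowest ladder a step 2 reactor would get 0.6 × 14.21 = 8.53 against a start of 10.53 mJ/cm². Under the alternative, the result may no longer be quoted on the MED scale.

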## 9 Study Procedures

We will advertise for this study at the Boston University Medical campus via email newsletters and advertisements on various TV screens. Once subjects have responded to the study flyer and contacted study staff, they will be screened over the phone to determine eligibility. During the preliminary screening telephone call, the subject will be asked about their medical history and inclusion/exclusion criteria. For the subjects who are determined to be eligible, they will be assigned with a study ID and their answers to the questions will be documented in the study binder. Eligible subject's contact information and identifier will be kept separate from the answers. For individuals with screening failure, no answer or identifiable information will be retained.

Eligible subjects be scheduled for their first visit to Boston University Medical Center's General Clinical Research Unit at [name] or in the clinical research space in the Vitamin D, Skin, and Bone Research Laboratory located at [name]. The study coordinator or IRB-approved research assistants will consent the subjects. [name] will not participate in consenting the subjects, but will be available to answer any questions or concerns that the subjects may have during the process. We will ask the subjects to read and ask any questions in regards to the screening

process that they have prior to signing the consent form. This consent form will also allow us to conduct a urine pregnancy test on women of child bearing potential, perform a 25(OH)D blood screen, and conduct our study experiment. Researchers will document that consent was given in our consent form log sheet where (s)he will need to sign and date that informed consent was given and that the subject received a copy of the ICF.

Approximately 14 adult subjects with 5 skin types groups (I, II, III, IV and V/ VI) will be enrolled for vitamin D deficiency/ insufficiency screening. We expect at least 80% of the population in the Boston area has a level of 25(OH)D below 30 ng/ml. Thus, we will enroll approximately 14 subjects with different group skin types to enroll 10 vitamin D deficient or insufficient subjects in this study. All of the subjects will receive the UVB intervention. The device will have a strip of colored LED installed inside the light towers. Both UV lamps and colored LED will turn on during the treatment. To elaborate further, all subjects will use the same device with the exact same workflow on the touchscreen user interface. The experience in starting a SOLIUS session, answering the safety questions, automatic dispensing of eyewear, etc. will be the same for all subjects. This is achieved by adding an independent software branch to the existing system that replicates the user workflow code but only turn on the LED drivers. LED strips are added to the existing light tower, and the lights will project through the same light path as the UV lamps. As a result, visible purple light will be emitted from the same emitting window as the UV lamps.

Blood samples will be obtained prior to the first titration (week 2), prior to the intervention (week 6) and end of the study. The blood samples for the screening will be performed by the Clinical Laboratory at Boston Medical Center which will be able to provide the test result within 24-48 hours. The blood samples for the study collected after screening, will be sent to Quest Diagnostics for determining the serum 25(OH)D levels. The study design is summarized in Table 2.

Each subject will be advised to come in for five titration visits. The purpose of these visits to establish the correct UVB dose in the SoliusONE device. At these visits, each subject will be asked questions about consumption of vitamin D, sun exposure, and whether he/she has had any adverse changes in his/her health. After the titration visit, each subject will complete a 4-week course of SoliusONE treatment. During each titration/treatment session, the study personnel will record subject's information in the application that is installed in the study personnel's smartphone. The information to be recorded include subject ID, age and sex. This allows the software to link to database and create user profiles for dosing. None of the identifiable information will be recorded in the application. Then, each subject will stand in the SoliusONE device while exposed to UVB light. Each subject will be asked to wear a swimsuit, swimming trunks (for males) or bikini (for females) while being exposed to UVB in the device. The device is large enough so that the participant is able to remove their clothing and to hang it up on a hook that is provided in the device. If they are wearing their bathing suit, they will then be exposed to the UVB light. If they have brought their bathing suit with them, they will be able to put it on in the device and then be exposed to the UVB light. They then have the option of keeping the bathing suit on and dressing or removing the bathing suit and putting on all of their undergarments and clothing before exiting the device. For those who either do not want to wear a bathing suit under their clothing or have forgot to bring their bathing suit then they will have the option of being exposed to the UVB in their underwear (males in their underwear shorts and females in their panties and bra). Each session will take approximately 2-10 minutes depending on the subject's skin type group (lighter skin type groups

require less treatment time). Before and after each treatment, the device will be cleaned using disinfectant to ensure proper hygiene.

Blood samples will be obtained from all subjects at baseline (prior to the first titration, week 2), prior to the intervention (week 6) and end of the study. Blood samples will be sent to Quest Diagnostics for determining the serum 25(OH)D levels. The study design summarized in Table 2

If a subject needs to end his/her regimen early they will be able to do so, with no change to the study procedure. We will require a final blood sample collection from the study subject prior to his/her removal.

We anticipate the entire study will take 6 months to complete. As discussed earlier the study subject's involvement will last 10 weeks from screening to completion include one week for screening, 5 weeks for titration, 4 weeks for treatment.

